#### **9.4.2 ANALYSIS OF THE PRIMARY EFFICACY ENDPOINT(S)**

Our primary analysis will evaluate the tissue visualization and quantitative accuracy of CBCT scans with 2D grid, as measured by objective image quality metrics. These metrics, namely absolute CT number error, artifact amplitude, and CNR, will be extracted from research CBCT

and standard clinical CBCT pairs of each study participant. In each CBCT image set, each metric will be measured from multiple ROIs, and their respective average values will be calculated. Subsequently, these values will be log transformed (natural logarithms) for the validity of normality. The Linear Mixed Effects model will be used to evaluate the differences in image quality metrics among CBCT types, while adjusting the random patients effect. The lower and upper limits of the 95% confidence interval will be calculated for each image quality metric and for each CBCT type. Image quality metrics of research CBCT scans and standard clinical CBCT scans will be compared in a pairwise fashion for the statistical significance of the differences between the two CBCT types. In a subgroup analysis, image quality metrics will be stratified into anatomical region groups and patient size groups to assess the effect of anatomical region and patient size on the image quality differences between the two CBCT types.

---

#### **9.4.3 ANALYSIS OF THE SECONDARY ENDPOINT(S)**

The analysis of this endpoint will be conceptually similar to primary endpoint, but this time, we will evaluate the consistency of delineations performed by automated software tools, which can greatly improve workflow efficiency in CBCT-based treatment monitoring. We will employ Machine Learning-based organ delineation and evaluate its accuracy with respect to observer-delineated structures.

Workflow: 1) Both research and standard clinical CBCT scans will be registered to helical CT images. After registration, observer-delineated structures will be also delineated independently by Machine Learning Methods. 2) Machine Learning based delineations will be compared to observer-generated delineations in CBCT scans. 3) We will use the similarity (i.e. CI and HD) and reliability (i.e. ICC) metrics to assess the consistency between Machine Learning-based and observer-generated delineations. The Machine Learning model for delineation will be selected by the PI, based on the availability of models for anatomical structures delineated by the observer.

---

#### **9.4.4 SAFETY ANALYSES**

This study does not include a formal safety endpoint, and therefore, safety analyses will not be performed.

---

#### **9.4.5 BASELINE DESCRIPTIVE STATISTICS**

The clinical and sociodemographic characteristics of all participants treated will be summarized using descriptive statistics (e.g. means/standard deviations, percentiles, frequencies). Participant characteristics within participant subgroups defined by the site of radiation treatment, the lateral separation groups, and the CBCT system types, will also be generated.

---

#### 9.4.6 PLANNED INTERIM ANALYSES

There will be no planned interim analyses.

---

##### 9.4.6.1 SUB-GROUP ANALYSES

1) Subgroup analyses of image quality metrics will be performed for three anatomical site groups:

- Head and Neck
- Pelvis and abdomen
- Prostate or prostate bed

2) A sub-group analysis of image quality metrics will be performed based on the patient size, as measured by the participant's lateral separation in the imaged volume:

- Lateral separation less than 30 cm
- Lateral separation between 30 and 40 cm
- Lateral separation more than 40 cm

3) Participants in the prostate group will be scanned using two substantially different CBCT systems. To investigate the effect of CBCT system on image quality, the following subgroups will be analyzed separately.

- Prostate and prostate bed subgroup scanned with photon therapy CBCT.
- Prostate and prostate bed subgroup scanned with proton therapy CBCT.

For each subgroup, image quality metrics extracted from CBCT scans with 2D grid and standard clinical CBCT scans will be compared in a pairwise fashion. 95% Confidence Intervals for the image quality metrics (primary objective) will be calculated and reported for each of the subgroups. And the pairwise comparisons between subgroups will be conducted by comparing the 95% Confidence Intervals.

---

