### 4 STUDY DESIGN

#### 4.1 OVERALL DESIGN

This is a Pilot study that investigates the CBCT image quality improvement provided by the 2D antiscatter grid technology. The primary objective is to assess the improvement in tissue visualization and CT number accuracy, as measured by objective image quality metrics.

- This is a single arm study, where all participants will be scanned with a CBCT system equipped with 2D antiscatter grid technology, referred to as research CBCT with 2D grid. Each participant will also be scanned with a standard clinical CBCT, which will serve as the baseline, or control. Thus, the image quality improvement in research CBCT with 2D grid will be assessed with respect to standard clinical CBCT without 2D grid.
- We anticipate enrolling a total of 42 participants. Groups (1) and (3) will have, in any combination, the collective total value of 21 participants. Group (2) will have 11

participants and Group (4) will have 10 participants. The groups are described as the following:

**Group (1), Photon therapy patients with treatment sites in abdomen or pelvis:** It is particularly challenging to use CBCT to visualize organ boundaries in the abdomen. Disease sites in the abdomen, e.g. the pancreas and liver, are particularly likely to benefit from “online” adaptive radiation therapy due to the proximity of the gastrointestinal tract to targets (online: plan is modified while the patient is on the treatment couch using volumetric setup images).

**Group (2), Photon therapy patients with treatment sites in prostate or prostate bed:** Due to the large tissue volume in the pelvis, scatter is more pronounced, and tissue visualization is degraded. Since larger patients generate more scatter, the image quality is also patient-size dependent. Hence, we will have two subgroups; subgroup stratification will be based on the patient left-right separation at pelvis level (subgroup 1:  $< 40$  cm, subgroup 2:  $\geq 40$  cm). 5 patients will be enrolled in subgroup 1 and 6 patients will be enrolled in subgroup 2. These “small” and “large” pelvis subgroups will allow evaluation of the effect of patient size on the consistency of organ delineation. The threshold of 40 cm comes from our clinical observations; CBCT images from patients with 40 cm (or more) separation are of noticeably lower quality.

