Analysis of radiomics feature extraction accuracy: In each image set, we will extract series of radiomics features, such as HU value statistics (e.g. mean, variance, and kurtosis), and texture features, such as gray-level co-occurrence matrix, wavelets, local entropy. Accuracy and repeatability of radiomics features in CBCT (both standard and 2D grid CBCT) and gold standard helical CT will be evaluated using Lin's concordance correlation coefficient (CCC) as in Zhao's work [35]. Statistical analysis details of other potential exploratory studies, such as qualitative and quantitative image quality evaluations, and CBCT-based dose calculations will be determined on an ad hoc basis.

The analysis of TrueBeam (Groups 1-3) and Proteus (Group 4) CBCT images. An image quality difference is expected between TrueBeam and Proteus CBCT due to differences in system design (e.g. TrueBeam has bow tie filter, whereas Proteus does not have one), and image reconstruction chain. Therefore, in the primary analysis, we will analyze the data from patient Groups 1-3 (TrueBeam) and Group 4 (Proteus) separately. This way, we will eliminate potential, system-specific image quality bias. In a subgroup analysis, we will investigate the differences in the study results of Groups 2 and 4 (i.e. prostate cancer patients scanned with TrueBeam and Proteus, respectively).

---

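### Size classes in 9.4.6.1 do not match the Group 2 enrolment strata in 4.1: exactly 40 cm is placed inconsistently, and the between-class size comparison may be confounded with anatomical site

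*Combined protocol and SAP*

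**What the plan says.** **Enrolment (4.1, Group 2).** After noting that larger patients scatter more and that image quality depends on size, the protocol creates two strata: "subgroup stratification will be based on the patient left-right separation at pelvis level", below 40 cm and 40 cm or more. The quotas are fixed: "5 patients will be enrolled in subgroup 1 and 6 patients will be enrolled in subgroup 2". The boundary value belongs to the large stratum, because "CBCT images from patients with 40 cm (or more) separation are of noticeably lower quality". The stated use is that these "subgroups will allow evaluation of the effect of patient size on the consistency of organ delineation".

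**Analysis (9.4.6.1, item 2).** Image quality metrics are analysed by size, "as measured by the participant's lateral separation in the imaged volume". There are three classes: "Lateral separation less than 30 cm", a middle class from 30 to 40 cm with neither endpoint assigned, and "Lateral separation more than 40 cm". The item is not limited to Group 2, to the pelvis or to one CBCT system. Site (item 1) and size (item 2) are separate one-way groupings. Subgroups are compared with each other by looking at their 95% confidence intervals.

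**Model (9.4.2).** The mixed model has CBCT type and a random patient effect; no site or size covariate is named. The declared aim of the subgroup analysis is to see how region and size affect the difference between the two CBCT types.

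**System (9.4.1).** For the primary analysis, "we will analyze the data from patient Groups 1-3 (TrueBeam) and Group 4 (Proteus) separately".

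**The concern.** Group 2 is the only group recruited to size quotas, yet the size analysis uses other cut-points, another measurement level and a pooled population. Three things follow.

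- The upper boundary is closed on one side at enrolment and on the other at analysis, so a 40 cm patient is classified against the protocol's own definition of large.
- The one within-site size comparison that enrolment was built to support is not planned anywhere. The delineation analysis named as its purpose is now exploratory (9.4.7) and lists subgroups by anatomical location only. The baseline tables in 9.4.5 mention lateral separation groups without saying which set.
- The aim in 9.4.2 needs a contrast between size classes. If the classes differ in site mix and nothing adjusts for it, a difference in grid benefit between small and large patients could be a difference between, say, head and neck and pelvis.

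At stake is the interpretation of a secondary question, how the grid benefit varies with patient size.

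**Working it through.** **1. Counts in the plan.** Group 2: 5 + 6 = 11. Photon total: 11 + 21 = 32. Study total: 32 + 10 = 42. All agree with 4.1.

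**2. Both rules applied to the same values**

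| Separation (cm) | Enrolment stratum (4.1) | Analysis class (9.4.6.1) |
|---|---|---|
| 29 | <40 | <30 |
| 39 | <40 | 30 to 40 |
| 40 | ≥40 | 30 to 40 if that endpoint is included, otherwise none |
| 41 | ≥40 | >40 |

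If the two measurements agree, only a recorded value of exactly 40 crosses the 40 cm line. Otherwise the analysis rule just splits the lower stratum at 30 cm. A value of exactly 30 has the same endpoint gap.

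**3. How many of the 6 large patients could read exactly 40.** The documents give no distribution and no recording precision, so both are assumed. Because the quota fixes 6 patients at a recorded 40 or more, the relevant probability is conditional. With recording width *w*:

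p = P(40 − w/2 < X < 40 + w/2) / P(X > 40 − w/2); expected number = 6p; chance of at least one = 1 − (1 − p)^6.

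Example, X normal with mean 38 and SD 3, w = 1: p = 0.106/0.309 = 0.34; 6p = 2.07; 1 − 0.656^6 = 0.92.

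| Assumed mean, SD (cm) | w = 1 cm: expected of 6 (chance of ≥1) | w = 0.1 cm: expected of 6 (chance of ≥1) |
|---|---|---|
| 37, 3 | 2.39 (95%) | 0.30 (26%) |
| 38, 3 | 2.07 (92%) | 0.25 (22%) |
| 38, 4 | 1.49 (82%) | 0.17 (16%) |
| 39, 4 | 1.29 (76%) | 0.14 (14%) |

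Over means of 36 to 40 and SDs of 3 to 5 cm, the ranges widen to 0.9-2.7 (62-97%) at 1 cm and 0.09-0.35 (9-30%) at 0.1 cm.

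**4. Site mix of the smallest class (Groups 1-3).** Section 4.1 lets Groups 1 and 3 share 21 places freely, so the head and neck number *h* is anywhere from 0 to 21. Let *a* be the share of head and neck patients under 30 cm and *b* the share of the others (both assumed). The head and neck share of the class is h·a / [h·a + (32 − h)·b].

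With h = 10:
- a = 100%, b = 0: 10/10 = 100%
- a = 80%, b = 5%: 8/(8 + 1.1) = 88%
- a = 50%, b = 10%: 5/(5 + 2.2) = 69%
- a = 20%, b = 10%: 2/(2 + 2.2) = 48%

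With h = 0 there are no head and neck patients in the class; with h = 21 the same four assumptions give 79-100%. Confounding with site can thus be absent or almost complete, and the plan does not fix which.

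**5. Precision of Group 2 by its own strata.** The 95% half-width, in SDs of the paired log difference, is t(0.975, n − 1)/√n: 2.776/√5 = 1.24 for n = 5 and 2.571/√6 = 1.05 for n = 6.

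**6. Whether a site-adjusted size term is feasible.** For paired scans, the CBCT type terms amount to regressing each patient's log difference on separation and site: 1 intercept + 1 slope + 2 site terms = 4 parameters, leaving 32 − 4 = 28 degrees of freedom if all 32 photon patients are evaluable.

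**The case against.** - **The quotas were not set for this analysis.** Section 4.1 ties them to delineation consistency, so other classes for image metrics do not contradict that purpose. This stands as far as it goes. But 4.1 also justifies the split by image quality at 40 cm, and the delineation analysis does not use the strata either.
- **The 40 cm cut survives.** If few prostate patients are under 30 cm, Group 2 falls into the middle and top classes, which is the enrolment split apart from ties at 40. This stands if the two measurement levels agree. The remaining gaps are the tie, the undefined endpoints and the pooling over sites.
- **Site effect.** A reader might infer that the size effect simply becomes a site effect, or that the size question cannot be answered. The documents do not support that: they give neither the head and neck number nor separations by site, and the middle and top classes can both hold prostate, pelvis and abdomen patients. Confounding is a risk of unknown extent.
- **Mixed systems.** A reader might infer that TrueBeam and Proteus patients will be combined in the size classes. Section 9.4.1 separates them in the primary analysis, and 9.4.6.1 item 3 does so again for prostate. Item 2 is silent, which is an ambiguity and not a plan to mix.
- **Size of the boundary problem.** A 76-95% chance that at least one patient moves holds only for whole-centimetre recording, which nothing in the plan states.
- **Small strata.** Groups of 5 and 6 will not give a firm answer under any rule. This stands, and is why the Group 2 result should be labelled descriptive.

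**Conclusion.** The mismatch is real and can be read directly from the two sections: different cut-points, different measurement levels, opposite handling of exactly 40 cm, and no stated analysis of the enrolment strata. None of this depends on an assumption. The number of patients affected at the boundary does: about 1 to 2 of 6 with 1 cm recording and about 0.1 to 0.3 of 6 with 0.1 cm recording, under assumed normal separations with means of 37-39 cm and SDs of 3-4 cm. The between-class size comparison may be confounded with site, to a degree that depends on a site mix and size distribution the documents leave open. Each class's comparison of grid and standard scans is made within patients, on the same system and day, so site does not confound it. The primary comparison is also unaffected. This should be corrected before analysis, but it does not threaten the main result.

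**What to change.** In 9.4.6.1 item 2:

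1. Define the classes as <30, 30 to <40 and ≥40 cm, so that the boundary matches 4.1. State one measurement level for each anatomical site and the recording precision.
2. Report the grid-versus-standard difference in Group 2 by its enrolment strata (<40 and ≥40 cm at pelvis level), labelled descriptive.
3. For Groups 1-3, replace the comparison of unadjusted confidence intervals with a CBCT type × lateral separation term in the mixed model, with anatomical site and its interaction with CBCT type also included.
4. State that Group 4 (Proteus) is kept separate in the size analysis, as in 9.4.1.

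The cost is revised wording and a few model terms. No new scans are needed, because separation is already required for enrolment and for the planned size classes. Two limits remain: the Group 2 intervals will be wide, and if site and separation hardly overlap in the enrolled patients, the adjusted size term will be imprecise and will lean on the assumed linear form. The report should show separation by site so that readers can judge this.

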### **Study intervention:**

In the photon therapy cohort, each study participant will receive one additional CBCT scan, with 2D antiscatter grid in place. This is the only intervention in the study, referred as research CBCT scan, and it will be performed on one of the days during the participant's radiation treatment course. This additional research CBCT scan will be used strictly for the objectives of this study. It will *not* be used as part of standard clinical care, such as imaging guidance of participant's radiation treatment or diagnostic purposes. To deliver participant's radiation treatment under CBCT guidance, a standard clinical CBCT scan will be acquired, as in standard clinical care protocols.

In the proton therapy cohort, each study participant will receive two additional CBCT scans, one with and the other without 2D antiscatter grid in place. The CBCT scan without 2D antiscatter grid will be equivalent to the standard clinical CBCT scan available in the proton therapy CBCT system. As in the photon therapy cohort, these images will not be used as part of standard clinical care. The participant's radiation treatment will be delivered by using the standard of care image guidance protocols in proton therapy.

The participant's involvement with the study will end with the completion of the study intervention. There will not be follow-up visits. Each participant's standard clinical CBCT scan will serve as the control. This way, image quality of research CBCT scans with 2D grid will be evaluated with respect to standard clinical CBCT scans. For each participant, imaging dose and technical parameters of the research CBCT scan will be identical to the standard clinical CBCT scan, and the two scans will be performed on the same day in either order.

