**1) Long range risks:** Participant will receive additional imaging dose due to one additional CBCT scan with 2D grid in the photon therapy cohort and two additional CBCT scans in the proton therapy cohort. Organ doses will be in the range of 0.5-3 cGy per scan in the photon therapy cohort and 1-1.5 cGy per scan in the proton therapy cohort [10]. In the context of radiation therapy, this is a very low level of radiation dose, and excess cancers have not been observed, or detectable, due to such a small increase in dose given to radiation therapy patients [11, 12].

While observed data does not exist, Dzierma et al. developed a model for excess cancer risk in pediatric radiation therapy patients due to CBCT scans [13]. They estimated that excess cancer risk is less than 0.2 cases per 10,000 person-years for 11 daily CBCT scans performed during radiation therapy. In our clinical trial, the excess risk due to research CBCT scan is expected to be significantly lower than Dzierma et al.'s estimate, since only one additional CBCT scan will be performed (as opposed to 11), and only adult patients will be accrued in our study, who have lower risk of secondary cancers due to radiation exposure [11, 14].

**2) Immediate risks:** While mechanical breakdown of the 2D grid has not happened during our experiments, there is a small chance that the 2D grid may break during a patient scan. To prevent the risk of bodily injury due to falling debris, grid prototypes will be checked for mechanical integrity before each scan, and a carbon-fiber protective enclosure will be placed on the grid during the scans.

---

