## 4.2 SCIENTIFIC RATIONALE FOR STUDY DESIGN

**Evaluation of CBCT image quality from a clinical perspective:** An essential clinical task in CBCT-guided radiation therapy is visualization of organ and tumor boundaries; clinicians often overlay MDCT images (acquired at treatment planning phase) and CBCT images (acquired at treatment delivery phase) to assess differences in tissue shapes and positions during the course of radiation therapy. Since these two image sets are acquired days or even weeks apart, geometric changes in tissue/organ boundaries between two image sets may imply under-dosing of tumors and/or over-dosing of normal tissues. In *better-quality* CBCT images, clinicians can visualize tissue boundaries more accurately and consistently.

Therefore, quality of research CBCT scans with 2D grid will be evaluated with respect to standard clinical CBCT scans without 2D grid (i.e., the control scan). Objective image quality metrics, such as absolute CT number error, artifact amplitude and contrast to noise ratio, will be extracted from each CBCT scan and the change in image quality metrics will be evaluated with

respect to the control scans. Similar studies have been performed to assess the quality of CBCT images in the context of image-guided radiation therapy [30, 31]. In addition, an observer study will be conducted, and consistency of tissue delineations by observers will be evaluated to assess the effect of CBCT image quality on tissue structure boundary visualization [32, 33].

Standard and research CBCT scans with 2D grid will be acquired on the same study participant, by using identical scan parameters. This approach addresses the following challenges associated with image quality comparisons.

- CBCT image quality depends on patient-specific factors such as patient size and shape, anatomical site of imaging study, and patient motion. By using the same patient and anatomical site for both standard and research scans, dependence of image quality on patient-specific variables is minimized.
- CBCT image quality depends on the imaging system characteristics and imaging dose. For each participant, both standard and research CBCT scans will be acquired using the same dose and scan parameters and using the same CBCT system. This approach minimizes dose and system specific effects on image quality.

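### Section 9.4.6.1 compares subgroups on metric levels, so a CNR comparison of Group 2 with Group 4 can report an imaging-dose difference as a system effect; the within-participant grid/standard ratio should be compared instead

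*Combined protocol and SAP*

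**What the plan says.** Section 9.4.6.1 lists three sets of subgroups: anatomical site, lateral separation, and CBCT system within prostate patients. For the third it states: "To investigate the effect of CBCT system on image quality, the following subgroups will be analyzed separately". Within each subgroup the grid and standard scans are compared pairwise. Then: "95% Confidence Intervals for the image quality metrics (primary objective) will be calculated and reported for each of the subgroups". The rule across subgroups is: "And the pairwise comparisons between subgroups will be conducted by comparing the 95% Confidence Intervals".

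Section 9.4.2 shows what those intervals are in the primary model: "The lower and upper limits of the 95% confidence interval will be calculated for each image quality metric and for each CBCT type". These are levels, one for each scan type. The same section gives a different aim for the site and size subgroups, namely "to assess the effect of anatomical region and patient size on the image quality differences between the two CBCT types". Section 2.1 (Study population) explains the proton cohort in similar terms: the effect of the grid may not be the same on the two kinds of system.

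On dose, Section 4.2 states: "CBCT image quality depends on the imaging system characteristics and imaging dose". Section 2.1 (Study intervention) states: "For each participant, imaging dose and technical parameters of the research CBCT scan will be identical to the standard clinical CBCT scan". Sections 4.2 and 4.3 repeat this matching. Step 5 of the scan overview in Section 6.1.1 has each participant scanned with his or her own clinical protocol. Section 2.3.1 puts organ doses "in the range of 0.5-3 cGy per scan in the photon therapy cohort and 1-1.5 cGy per scan in the proton therapy cohort". Neither the CNR formula in Section 9.4.1, nor the model in 9.4.2, nor the subgroup rule in 9.4.6.1 contains a dose term.

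**The concern.** The paired design protects the grid-versus-standard contrast: same person, same system, same dose. That protection is lost once the CNR level in one subgroup is set against the level in another. CNR has image noise in its denominator, and noise ordinarily falls as dose rises. A group scanned at higher dose would then show higher CNR whatever the system.

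The system comparison is the most exposed. Its stated purpose concerns image quality itself and does not mention the grid-versus-standard difference. Section 9.4.1 already expects the two systems to differ because of system design and reconstruction, so a gap in CNR would naturally be read that way. What is at stake is whether the comparison of Group 2 with Group 4 can support any statement about the systems. The plan offers no means to detect or remove a dose gap if there is one.

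**Working it through.** The plan gives no figure for the subgroup comparisons, so there is none to reproduce.

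**Inputs from the documents.** Organ dose per scan: photon 0.5 to 3 cGy, proton 1 to 1.5 cGy (Section 2.3.1). Prostate participants: 11 photon, 10 proton (Sections 2.1 and 4.1). Metrics are analysed on the natural-log scale (Section 9.4.2). The grid doubled CNR in pelvis-sized phantoms (Section 2.2), which serves as a yardstick.

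**Assumptions.** CNR is proportional to the square root of dose (quantum-limited noise). Between-participant SD of log CNR is 0.2 to 0.4 and within-participant SD is 0.15. The SD of a single scan is then √(0.2² + 0.15²) = 0.25 to √(0.4² + 0.15²) = 0.43. The true grid effect is the same in both groups, and there is no system effect.

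**Step 1: how far dose alone could move CNR.** CNR ratio = √(dose ratio).
- Photon v proton, lowest: √(0.5/1.5) = 0.58.
- Photon v proton, highest: √(3/1) = 1.73.
- Equal dose: √1 = 1. This is also possible, because the proton range lies inside the photon range.

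The upper extreme is of the same order as the phantom gain of 2.

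**Step 2: how often levels would appear to differ.** Simulation, 40,000 runs, 11 v 10 participants, t-based 95% intervals of log CNR on the grid scans. The groups are called different if the intervals do not overlap. The log shift is 0.5 × ln(dose ratio), which is 0.5 × ln 2 = 0.35 at a 2-fold gap.

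| Between-participant SD | Equal dose | 1.5-fold | 2-fold | 3-fold |
|---|---|---|---|---|
| 0.2 | 0.5% | 13.1% | 53.5% | 95.7% |
| 0.3 | 0.6% | 6.4% | 25.8% | 71.9% |
| 0.4 | 0.5% | 3.7% | 13.7% | 44.9% |

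**Step 3: the same trials on the paired log ratio.** With log CNR = participant effect + 0.5 × ln(dose) + grid effect + error, subtracting the standard scan from the grid scan removes both the participant effect and the dose term. The non-overlap rate is 0.5% to 0.6% at every dose ratio tried, from 1/3 to 3.

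**Step 4: does the ratio remove dose completely?** Only if all the noise depends on dose. Suppose that 25% of the noise variance of the standard scan at reference dose does not depend on dose, and that the grid cuts this part four-fold. At relative dose D, the grid/standard CNR ratio is √[(0.75/D + 0.25)/(0.75/D + 0.0625)].
- D = 1: √(1/0.8125) = 1.11.
- D = 2: √(0.625/0.4375) = 1.20.
- D = 3: √(0.5/0.3125) = 1.26.

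At double dose the ratio moves by a factor of 1.195/1.109 = 1.08, compared with 1.41 (√2) for the level under pure square-root scaling. Most of the dose effect goes, but not necessarily all.

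**The case against.** The best defence is that the plan never intended to compare levels. Section 9.4.2 gives the aim for site and size as the effect on the difference between scan types, a dose-matched contrast. Section 2.1 gives a similar reason for enrolling the proton cohort. Section 9.4.1 speaks only of differences in the study results of Groups 2 and 4, and the study's main result is grid versus standard. On that view the fault is loose wording in 9.4.6.1. Much of this stands, and it is why the remedy should lead with the paired ratio. It does not close the point: the operative rule still names intervals of the metrics, the aim in 9.4.2 names region and size but not system, and item 3 is worded as a question about image quality.

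A reader might infer that a dose difference will in fact be reported as a system, site or size effect. The documents do not support that. The doses in Section 2.3.1 are organ doses for whole cohorts, not broken down by site, size or prostate group. The ranges overlap, and equal dose in Groups 2 and 4 is consistent with them. The 2- and 3-fold gaps and all the SDs above are assumptions.

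Two further objections also stand. Comparing systems as they are clinically operated, protocol dose included, is a legitimate descriptive question. And dividing CNR by the square root of dose could itself create a false difference if noise is not purely dose-driven, or if the two systems have no common dose index; the documents establish neither condition.

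**Conclusion.** The point holds in a limited form. Section 9.4.6.1 as written compares levels, while Sections 9.4.2 and 2.1 point to the grid-versus-standard difference as the quantity of interest. For CNR, and most clearly for Group 2 against Group 4, a comparison of levels cannot separate system from dose.

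If the groups differ 2-fold in dose, a spurious difference appears in roughly 14% to 53% of trials by the plan's interval rule, and in 45% to 96% at 3-fold, against about 0.6% on the paired ratio. These rates rest on square-root scaling, the assumed SDs and the assumed gap. With equal dose there is no dose confounding.

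For site and size, the stated aim is already the dose-matched contrast, so the rule needs only to be brought into line with it. It would also be wrong to infer that the primary result is compromised: it is paired and dose-matched, and the two systems are analysed separately. The change is worth making because it alters what the subgroup analysis can conclude, not because the trial's main answer is in doubt.

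**What to change.** In Section 9.4.6.1:

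1. Compare subgroups on the within-participant log ratio (2D grid over standard) of each metric, through a subgroup-by-CBCT-type interaction reported with its 95% confidence interval, in place of comparing intervals of levels. State that the ratio is relative to each system's own standard scan. The interaction test will have its nominal 5% error rate; the 0.6% above belongs to the non-overlap rule.
2. Carry an exposure or dose index for each scan into the analysis dataset. The Section 6.4 checklist confirms matching of parameters but is not described as supplying an analysis variable.
3. Where CNR levels are shown across systems, label raw CNR as describing the systems as clinically operated. Put dose-normalised CNR beside it if a common index exists for both systems, and do not attribute raw differences to the system.

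The cost is a few sentences in the plan, one extra variable and a little more analysis. Normalisation rests on a noise assumption, so it should accompany raw CNR and not replace it. No scan, dose setting or enrolment number changes.
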